**Table 11. Additional Dose Modification Guidelines for Axitinib.**

\*NOTE: if patient starts with grade 2 LFT elevation (liver metastases), any increase of  $\geq$  to 50% of baseline that does not resolve within 7 days is considered grade 3 toxicity and patients should be dose reduced as above.

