Renal	
Serum creatinine OR Measured or calculated a creatinine clearance (GFR can also be used in place of creatinine or CrCl)	≤1.5 X upper limit of normal (ULN) OR  ≥60 mL/min for subject with creatinine levels > 1.5 X institutional ULN
Hepatic	
Serum total bilirubin	≤ 1.5 X ULN OR Direct bilirubin ≤ ULN for subjects with total bilirubin levels > 1.5 ULN
AST (SGOT) and ALT (SGPT)	≤ 2.5 X ULN OR ≤ 5 X ULN for subjects with liver metastases
Albumin	≥2.5 mg/dL
Coagulation	
International Normalized Ratio (INR) or Prothrombin Time (PT)	≤1.5 X ULN unless subject is receiving anticoagulant therapy as long as PT or PTT is within therapeutic range of intended use of anticoagulants
Activated Partial Thromboplastin Time (aPTT)	≤1.5 X ULN unless subject is receiving anticoagulant therapy as long as PT or PTT is within therapeutic range of intended use of anticoagulants
a Creatinine clearance should be calculated per institutional standard.	

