#### Lab Toxicity

AE	Patient Population	Dose Limiting Toxicity
Anemia (Hemoglobin)	All	<6.5 g/dl
Platelet count decreased	All	Grade 4 (<25,000mm  )
Febrile neutropenia	All	≥ Grade 3
Acute kidney injury	Does not resolve within 7 days	≥ Grade 3 (>3 x above baseline)
Proteinuria	Does note resolve within 7 days	≥ Grade 3
Liver function abnormalities (transaminitis/hyperbilirubinemia)	If grade 2 (>1.5 - 3.0 x ULN ) at baseline, than any ≥50% increase from baseline that does not resolve within 7 days	>5 x ULN

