## 10.0 TREATMENT/ DOSE MODIFICATIONS

### 10.1 Unacceptable Toxicity

Causality for all adverse events should be assessed and if deemed attributable, attempts should be made to attribute to either axitinib, pembrolizumab, or potentially both agents.

In the case of toxicities refractory to routine medical management which are assessed as possibly attributable to both drugs (i.e. liver enzyme elevation, renal dysfunction, thyroid dysfunction, diarrhea/colitis) that may be autoimmune in origin, dose interruption of axitinib should be attempted first. Generally prompt resolution of the toxicity is observed if attributable to axitinib. If the toxicity is persistent, treatment should be administered as per the pembrolizumab treatment guidelines below, including corticosteroid therapy where advised.

Drug-related grade 4 toxicities will generally require subject to discontinue all study treatment. Exceptions include the following: 1) clear evidence that the toxicity was attributable to axitinib alone, resolved upon cessation of axitinib, and there is rationale to continuing pembrolizumab monotherapy 2) Grade 4 lab abnormalities that are not immune-related, where the patient is asymptomatic, and the abnormalities can be reversed with medical treatment. Example: grade 4 hypertriglyceridemia that responds to antilipid drugs. Intolerable grade 2 and grade 3 toxicities should be managed as per dose modification guidelines listed in the tables below. For grade 2 and grade 3 toxicities attributable to axitinib that do not resolve to  $\leq$  grade 1 within 3 weeks of holding study drug, axitinib should be permanently discontinued. Pembrolizumab therapy may be continued providing the residual adverse events are within permissible ranges for pembrolizumab dosing.

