Proteinuria	2	Continue treatment if asymptomatic and not associated with creatinine rise. If accompanied by renal insufficiency or evidence of nephritis, refer to pembrolizumab guidelines for treatment and hold axitinib until $\leq$ grade 1.	If isolated proteinuria, no dose reduction. If associated with AKI/nephritis, dose reduce one dose level after resolution to $\leq$ grade 1.
	3	Hold axitinib until $\leq$ grade 1. Refer to pembrolizumab guidelines as per grade 2.	Dose reduce one dose level
Elevation of liver enzymes or bilirubin	2/3	Hold axitinib until $\leq$ grade 1. *	Dose reduce one dose level.
	4	Discontinue axitinib	Discontinue axitinib.
Other toxicity	2	Intolerable grade 2 toxicity, may hold axitinib or dose-reduce at physician discretion.	May hold axitinib or dose-reduce at physician discretion.
	3	Hold until resolution to $\leq$ grade 1	Dose reduce one dose level.
	4	Discontinue axitinib	Discontinue axitinib.

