	Grade 3 or 4	Withhold or permanently discontinue 		
Hypothyroidism	Grade 2-4	Continue	Initiate thyroid replacement hormones (eg, levothyroxine or liothyronine) per standard of care	Monitor for signs and symptoms of thyroid disorders.
Nephritis and Renal dysfunction	Grade 2	Withhold	Administer corticosteroids (prednisone 1-2 mg/kg or equivalent) followed by taper.	Monitor changes of renal function
	Grade 3 or 4	Permanently discontinue		
Myocarditis	Grade 1 or 2	Withhold	Based on severity of AE administer corticosteroids	Ensure adequate evaluation to confirm etiology and/or exclude other causes
	Grade 3 or 4	Permanently discontinue		
All other immune-related AEs 	Intolerable/persistent Grade 2	Withhold	Based on type and severity of AE administer corticosteroids	Ensure adequate evaluation to confirm etiology and/or exclude other causes
	Grade 3	Withhold or discontinue based on the type of event. Events that require discontinuation include and not limited to: Gullain-Barre Syndrome, encephalitis		
	Grade 4 or recurrent Grade 3	Permanently discontinue		

1. Withhold or permanently discontinue pembrolizumab is at the discretion of the investigator or treating physician.
 
2. For grade 3 liver toxicity with elevated AST and/or ALT. Since HCC patients may have grade 1-2 elevation of AST/ALT at baseline, if these patients have Grade 3 elevation of AST/ALT, hold therapy and resume treatment when AST/ALT return to baseline or Grade ≤1. The AST/ALT should return to baseline or < 5 x ULN within 12 weeks from start of grade 3, otherwise patient should be discontinued from study.
 
3. Patients with intolerable or persistent Grade 2 drug-related AE may hold study medication at physician discretion. Permanently discontinue study drug for persistent Grade 2 adverse reactions for which treatment with study drug has been held, that do not recover to Grade 0-1 within 12 weeks of the last dose.
 
NOTE: For participants with Grade 3 or 4 immune-related endocrinopathy where withhold of pembrolizumab is required, pembrolizumab may be resumed when AE resolves to ≤ Grade 2 and is controlled with hormonal replacement therapy or achieved metabolic control (in case of T1DM).
				

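### Axitinib restart after a liver-test rise requires grade 1 or below, with no return-to-baseline option for patients who entered at grade 2

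*Combined protocol and SAP*

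**What the plan says.** Four parts of the protocol bear on a patient who enters with raised liver tests.

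- **Eligibility (5.1, criterion 11, Table 2).** AST and ALT may be "≤ 5 X ULN for subjects with liver metastases". Table 4 (section 7.2) also provides for patients at grade 2 at baseline, with a band of above 1.5 to 3.0 × ULN, and refers to "than any ≥50% increase from baseline that does not resolve within 7 days".
- **The NOTE under Table 11 (10.2).** It applies "if patient starts with grade 2 LFT elevation (liver metastases"). A rise of at least 50% over baseline, unresolved at 7 days, "is considered grade 3 toxicity and patients should be dose reduced as above".
- **The Table 11 row "Elevation of liver enzymes or bilirubin".** For grade 2 or 3, axitinib is held until grade 1 or below and then reduced one dose level. An asterisk on the hold instruction links the row to the NOTE.
- **Section 10.1.** For grade 2 and 3 toxicity attributed to axitinib that has not come down to at most "grade 1 within 3 weeks of holding study drug, axitinib should be permanently discontinued". Only axitinib stops: "Pembrolizumab therapy may be continued providing the residual adverse events are within permissible ranges for pembrolizumab dosing".

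The row, the NOTE and section 10.1 give no return-to-baseline alternative for restarting axitinib.

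**The concern.** The trigger is relative to the patient's own baseline, while the restart test is an absolute grade. A patient who enters at grade 2 is by definition above grade 1, so complete reversal of the on-treatment rise still leaves the restart test unmet. The NOTE intends continued axitinib at a lower dose. The row and section 10.1, taken literally, keep the drug on hold and then end it.

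Two investigators could therefore manage the same recovered patient differently. One would restart axitinib a level lower; the other would stop one of the two study drugs for a rise that has already reversed. Section 16.3 reports how many patients discontinue therapy and why, so such stops would appear in the toxicity summary as a product of the rule's wording.

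**Working it through.** The plan states no figure here, so there is nothing to reproduce. The check compares the trigger with the restart threshold.

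**Inputs**
- Entry value *b*, in multiples of ULN, inside Table 4's grade 2 baseline band (above 1.5 to 3.0).
- Top of grade 1, *c* = 1.5 × ULN, taken as the lower edge of that band.
- NOTE trigger: a 50% rise, so 1.5*b*.

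**Formulas**
- Fall below the entry value needed to restart: 1 − *c*/*b*.
- Fall from trigger back to entry: 1 − 1/1.5 = 33.3%, whatever *b* is.
- Fall from trigger to the restart threshold: 1 − *c*/(1.5*b*).

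| Entry *b* (× ULN) | Trigger 1.5*b* | Needed below entry | Trigger to entry | Trigger to restart |
|---|---|---|---|---|
| 2.0 | 3.0 | 1 − 1.5/2.0 = 25% | 33.3% | 1 − 1.5/3.0 = 50% |
| 2.5 | 3.75 | 1 − 1.5/2.5 = 40% | 33.3% | 1 − 1.5/3.75 = 60% |
| 3.0 | 4.5 | 1 − 1.5/3.0 = 50% | 33.3% | 1 − 1.5/4.5 = 66.7% |

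**Dependence on the band.** Table 4 groups transaminases with bilirubin, and its band may differ from the CTCAE v4.03 cut-offs for AST/ALT, which the documents do not reproduce. As an assumption only, take a grade 2 band of above 3.0 to 5.0 × ULN. An entry value of 5.0 would then trigger at 7.5 and need 3.0 or less to restart, which is 1 − 3.0/5.0 = 40% below entry. The percentages move with the band but the direction does not: grade 2 means *b* > *c*, so 1 − *c*/*b* is positive for every grade 2 entrant.

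**Timing.** The NOTE does not define what it means to resolve. If it means return to entry value, a patient who returns by day 7 needs no action under the NOTE. The same return some days later falls under the hold, with no written way back to axitinib.

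**Other recovery rules in the protocol.** Exclusion criteria 4 and 5 accept recovery to grade 1 or to baseline after earlier therapy. Footnote 2 to Table 12, for pembrolizumab, says to "hold therapy and resume treatment when AST/ALT return to baseline or Grade" 1 or below. Both are imperfect comparators, since the first concerns prior treatment and the second names HCC patients. They do show that a baseline alternative is familiar to this protocol.

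**The case against.** A reader might infer that the NOTE and the liver row contradict each other. They do not. The NOTE's closing words point back to the row, so the two can be read in sequence: grade the rise against baseline, then hold and reduce. What remains is a restart threshold that does not fit the population the NOTE describes.

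The strongest defence is discretion. Section 8.5.1 leaves resumption after an adverse-event hold to the investigator, footnote a to Table 10 refers other drug-related events to the table and the principal investigator, and Table 11 is titled as guidelines. This makes a sensible outcome likely. But section 8.5.1 ties the discretion to the section 10.0 guidelines, and those are the text that lacks the alternative.

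A second defence is attribution. The 3-week clause covers only axitinib-attributable toxicity, and section 15.4 limits adverse events to those that begin or worsen on treatment. Once values are back at entry, what is left is arguably the pre-existing elevation. This weakens the inference that a permanent stop is compulsory. It does not reach the liver row, whose hold ends at an absolute grade. The definition of resolution in section 15.4, which does mention baseline, governs adverse-event follow-up, not drug restart.

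Third, the grade 1 threshold looks deliberate: the revision history for version 4.0 describes it. That entry says nothing about patients who start at grade 2.

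Finally, a reader might infer that in cycle 1 the same rise is always a DLT, so that section 11.0 already permits stopping. Table 4's layout does not settle this. The 50% rise sits in the patient-population column, the DLT column says above 5 × ULN, and all three triggers computed here are below that.

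**Conclusion.** The point holds, as a minor gap in a dosing rule. For patients who enter at grade 2, the written axitinib restart test is stricter than their own entry value under any grade 2 band: by 25%, 40% or 50% at entry values of 2.0, 2.5 or 3.0 × ULN if Table 4's band applies. This rests on a literal reading of the liver row and of section 10.1; an investigator using discretion could avoid the outcome.

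Three larger inferences are not supported. The documents do not give the number of patients with grade 2 liver tests at entry, so neither a count affected nor a statement that it is negligible can be derived. All study treatment does not stop, because section 10.1 lets pembrolizumab continue. No power or error rate changes.

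**What to change.** In the grade 2/3 liver row of Table 11 and in the 3-week clause of section 10.1, write: *≤ grade 1, or return to baseline for patients who entered with grade 2 liver tests*, then restart axitinib one dose level lower. If the sponsor prefers the strict rule for these patients, it should say so explicitly in the NOTE; that also removes the ambiguity.

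The cost is a few words in two places. No tests, visits or patients are added, since the metabolic panel is already scheduled throughout treatment.

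The downside is a slightly less strict hepatic restart. Section 9.1.4 reports about 2-fold higher axitinib exposure in moderate hepatic impairment, and section 1.3 mentions hepatic failure with another TKI plus PD-1 combination. The added risk is limited because these patients were allowed to start at the full 5 mg twice daily with the same liver values, and would restart a level below their dose at the time of the event. That reassurance is weaker for a patient already escalated to 7 mg or more, whose next level down (6 mg or more) is still above the starting dose.

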### **10.3 Dose Modification Guidelines for Pembrolizumab**

Adverse events (AEs) both serious and non-serious associated with pembrolizumab exposure may represent an immunologic etiology. These AEs may occur shortly after the first dose or several months after the last dose of treatment. Pembrolizumab must be withheld for drug-related toxicities and severe or life-threatening AEs as per Table 10 below. See also Section 8.4 for supportive care guidelines and Appendix H.

Dosing interruptions are permitted in the case of medical/surgical events or logistical reasons not related to study therapy (e.g. elective surgery, unrelated medical events, patient vacation, and/or holidays). Subjects should be placed back on study therapy within 3 weeks of the scheduled interruption, unless otherwise discussed with the PI. The reason for the interruption should be documented in the patient's study record.

**Table 12. Dose Modification and Toxicity Management Guidelines for Immune-Related AEs Associated with Pembrolizumab.**

General instructions:				

 
1. Corticosteroid taper should be initiated upon AE improving to Grade 1 or less and continue to taper over at least 4 weeks.
 
2. For situations where pembrolizumab has been withheld, pembrolizumab can be resumed after AE has been reduced to Grade 1 or 0 and corticosteroid has been tapered. Pembrolizumab should be permanently discontinued if AE does not resolve within 12 weeks of last dose or corticosteroids cannot be reduced to <math>\leq 10</math> mg prednisone or equivalent per day within 12 weeks.
 
3. For severe and life-threatening irAEs, IV corticosteroid should be initiated first followed by oral steroid. Other immunosuppressive treatment should be initiated if irAEs cannot be controlled by corticosteroids.
 
				
Immune-related AEs	Toxicity grade or conditions (CTCAEv4.0)	Action taken to pembrolizumab	irAE management with corticosteroid and/or other therapies	Monitor and follow-up
Steven-Johnson Syndrome (SJS)	Any	Permanently discontinue	Refer patient for specialized care for assessment and treatment.	If SJS confirmed, permanently discontinue pembrolizumab
Toxic Epidermal Necrolysis (TEN)	Any	Permanently discontinue	Refer patient for specialized care for assessment and treatment.	If TEN confirmed, permanently discontinue pembrolizumab
Pneumonitis	Grade 2	Withhold	Administer corticosteroids (initial dose of 1-2 mg/kg prednisone or equivalent) followed by taper	
Monitor participants for signs and symptoms of pneumonitis
 
Evaluate participants with suspected pneumonitis with radiographic imaging and initiate corticosteroid treatment
 
Add prophylactic antibiotics for opportunistic infections

	Grade 3 or 4, or recurrent Grade 2	Permanently discontinue		
Diarrhea / Colitis	Grade 2 or 3	Withhold	Administer corticosteroids (initial dose of 1-2 mg/kg prednisone or equivalent) followed by taper	
 
• Monitor participants for signs and symptoms of enterocolitis (ie, diarrhea, abdominal pain, blood or mucus in stool with or without fever) and of bowel perforation (ie, peritoneal signs and ileus).
 
• Participants with <math>\geq</math> Grade 2 diarrhea suspecting colitis should consider GI consultation and performing endoscopy to rule out colitis.
 
• Participants with diarrhea/colitis should be advised to drink liberal quantities of clear fluids. If sufficient oral fluid intake is not feasible, fluid and electrolytes should be substituted via IV
 

	Grade 4	Permanently discontinue		infusion.
AST / ALT elevation	3	Withhold	Administer corticosteroids (initial dose of 0.5- 1 mg/kg prednisone or equivalent) followed by taper	Monitor with liver function tests (consider weekly or more frequently until liver enzyme value returned to baseline or is stable
	4	Permanently discontinue --see exception below 	Administer corticosteroids (initial dose of 1-2 mg/kg prednisone or equivalent) followed by taper	
Increased bilirubin	Grade 2	Withhold	Administer corticosteroids (initial dose of 0.5- 1 mg/kg prednisone or equivalent) followed by taper	Monitor with liver function tests (consider weekly or more frequently until liver enzyme value returned to baseline or is stable
	Grade 3 or 4	Permanently discontinue	Administer corticosteroids (initial dose of 1-2 mg/kg prednisone or equivalent) followed by taper	
Type 1 diabetes mellitus (T1DM) or Hyperglycemia	Newly onset T1DM or Grade 3 or 4 hyperglycemia associated with evidence of $\beta$ -cell failure	Withhold	Initiate insulin replacement therapy for participants with T1DM  Administer anti-hyperglycemic in participants with hyperglycemia	Monitor participants for hyperglycemia or other signs and symptoms of diabetes.
Hypophysitis	Grade 2	Withhold	Administer corticosteroids and initiate hormonal replacements as clinically indicated.	Monitor for signs and symptoms of hypophysitis (including hypopituitarism and adrenal insufficiency)
	Grade 3 or 4	Withhold or permanently discontinue 		

Hyperthyroidism	Grade 2	Continue	Treat with non-selective beta-blockers (eg, propranolol) or thionamides as appropriate	Monitor for signs and symptoms of thyroid disorders.
	Grade 3 or 4	Withhold or permanently discontinue 		
Hypothyroidism	Grade 2-4	Continue	Initiate thyroid replacement hormones (eg, levothyroxine or liothyronine) per standard of care	Monitor for signs and symptoms of thyroid disorders.
Nephritis and Renal dysfunction	Grade 2	Withhold	Administer corticosteroids (prednisone 1-2 mg/kg or equivalent) followed by taper.	Monitor changes of renal function
	Grade 3 or 4	Permanently discontinue		
Myocarditis	Grade 1 or 2	Withhold	Based on severity of AE administer corticosteroids	Ensure adequate evaluation to confirm etiology and/or exclude other causes
	Grade 3 or 4	Permanently discontinue		
All other immune-related AEs 	Intolerable/persistent Grade 2	Withhold	Based on type and severity of AE administer corticosteroids	Ensure adequate evaluation to confirm etiology and/or exclude other causes
	Grade 3	Withhold or discontinue based on the type of event. Events that require discontinuation include and not limited to: Gullain-Barre Syndrome, encephalitis		
	Grade 4 or recurrent Grade 3	Permanently discontinue		

1. Withhold or permanently discontinue pembrolizumab is at the discretion of the investigator or treating physician.
 
2. For grade 3 liver toxicity with elevated AST and/or ALT. Since HCC patients may have grade 1-2 elevation of AST/ALT at baseline, if these patients have Grade 3 elevation of AST/ALT, hold therapy and resume treatment when AST/ALT return to baseline or Grade ≤1. The AST/ALT should return to baseline or < 5 x ULN within 12 weeks from start of grade 3, otherwise patient should be discontinued from study.
 
3. Patients with intolerable or persistent Grade 2 drug-related AE may hold study medication at physician discretion. Permanently discontinue study drug for persistent Grade 2 adverse reactions for which treatment with study drug has been held, that do not recover to Grade 0-1 within 12 weeks of the last dose.
 
NOTE: For participants with Grade 3 or 4 immune-related endocrinopathy where withhold of pembrolizumab is required, pembrolizumab may be resumed when AE resolves to ≤ Grade 2 and is controlled with hormonal replacement therapy or achieved metabolic control (in case of T1DM).
				

## 11.0 TREATMENT DISCONTINUATION

Treatment may be discontinued for any of the following reasons:

- The patient experiences a DLT
- The patient demonstrates radiologic progression by RECIST 1.1. **(See exception below).**
- The patient withdraws consent from the study
- The patient has not received study treatment for >21 days due to a medical/surgical events or logistical reasons not related to study therapy (e.g. elective surgery, unrelated medical events, patient vacation, and/or holidays).
- The patient has completed 24 months of uninterrupted treatment with pembrolizumab or 35 administrations of study medication, whichever is later.
- The patient experiences an adverse event that in the opinion of the Investigator makes continued study treatment an unacceptable risk
- The patient becomes pregnant (also see Section 15.6 and Appendix A for Expedited Adverse Event Reporting Requirements)
- The patient requires continuous treatment with a prohibited concomitant drug(s) for which no safe alternatives can be substituted
- The patient is significantly noncompliant with the requirements of the protocol

**Exception: Patients who exhibit radiologic progression by RECIST 1.1 may remain on the study if in the opinion of the Investigator, he/she is deriving clinical benefit from study treatment, particularly if response assessment by immune-related RECIST criteria, Choi criteria, or MRI volumetrics would not require discontinuation. A follow up confirmatory scan should be scheduled in 6 weeks. For later analysis of the primary endpoint, assuming that the confirmatory scan ALSO shows RECIST progression, the initial scan will be recorded as the first date of progression.**

Should discontinuation of study therapy occur, all efforts should be made to execute/ report End-of-Treatment and Follow-up Evaluations as completely as possible and to determine/ document the reason for discontinuation (unless the patient withdraws consent for follow-up).

If a patient wishes to withdraw consent from the study, the PI must be notified. The information regarding withdrawal (i.e. subject identifiers and date of withdrawal) should be documented in the subject's record and updated within any other research database(s).

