While the official endpoint for this trial of concurrent axitinib/pembrolizumab in sarcomas will utilize RECIST v1.1, tumor response will also be assessed in parallel using Choi criteria and immune-related response criteria for patients utilizing CT for serial imaging, or modified Choi criteria and MRI volumetrics using dynamic contrast enhanced MRI sequences for patient being followed with MRI. All patients will also have a pre-treatment PET/CT, and those patients with a positive PET at baseline will undergo additional on-treatment PET imaging. The results from these non-traditional methods will be used to design future clinical trials in sarcoma in order to more accurately assess tumor response, particularly in the setting of immunotherapy.

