### **14.2 Progression-Free Survival (PFS)**

Patients will be evaluated during treatment and by follow-up assessments post-treatment at: 30-days (+5 days). PFS is defined as the time from treatment initiation until documented disease progression or death (by any cause, in the absence of progression). In progression-free patients, PFS will be censored at the last evaluable tumor assessment (RECIST v1.1).

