#### Endpoints

The primary endpoint will be the progression-free survival by RECIST 1.1 in evaluable patients treated with combination axitinib/pembrolizumab.

The secondary endpoints include:

- The objective response rate (ORR) is defined as the proportion of patients whose response by RECIST 1.1 is complete response (CR) or partial response (PR). The clinical benefit rate (CBR) is the proportion of patients whose response by RECIST 1.1 is complete response (CR), partial response (PR), or stable disease (SD). The time to progression (TTP) is defined as time from treatment initiation to first occurrence of progression by RECIST v1.1 or death of sarcoma patients treated with concurrent axitinib/pembrolizumab therapy. Overall survival (OS) is defined as the elapsed time from treatment initiation to death from any cause, whichever is earlier. Patients alive or those lost to follow-up will be censored at the last date of contact (or last date known to be alive).
- Adverse events, including dose-limiting toxicity and grade 3 or grade 4 serious adverse events
  - DLT includes treatment-related (possible, probably, or definite) grade 3 or higher toxicities as detailed in section 7.2. Toxicity will be reported by short name, type, grade, and attribution as per CTCAE v4.0.3.

The exploratory endpoints include:

- The quantity of CD3+ T-cells in peripheral blood and in tumor biopsies at each timepoint (baseline, cycle 3, and off-study).
- The expression category in tumor tissue (none (0%), low (<5%), intermediate (5-50%), or high (>50%) of various markers including PD-1, PD-L1, PD-L2, CTLA-4, TIM-3, LAG-3 at each timepoint (baseline, cycle 3, and off-study).
- The following T cell subsets will be studied in peripheral blood and tumor tissue: (CD4, CD8, T-reg, CTLA4, TIM3, LAG3, memory, naïve, PD-1, Ki67). For each marker, the absolute change in the marker(s) value will be calculated:
  - Cycle 3 marker value minus Baseline marker value
  - Progression marker value minus Cycle 3 marker value
  - Progression marker value minus Baseline marker value
- For each of the alternative (non-RECIST) radiological measurements we will categorize tumor response as CR/PR/SD vs PD. CT and/or MRI with dynamic contrast enhanced sequences will be collected throughout the study at every disease evaluation and analyzed using Choi criteria, MRI volumetrics, and

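### Section 11.0 makes the primary progression date depend on a 6-week confirmatory scan for patients kept on treatment and leaves the unconfirmed case unstated, in conflict with the RECIST 1.1 definition of PFS elsewhere

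*Combined protocol and SAP*

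**What the plan says.** Section 11.0 lists RECIST 1.1 progression among the reasons for stopping treatment and then gives an exception. A patient with such progression "may remain on the study if in the opinion of the Investigator, he/she is deriving clinical benefit from study treatment". The exception adds: "A follow up confirmatory scan should be scheduled in 6 weeks". It then moves from treatment to analysis and says how the primary endpoint is to be dated: "assuming that the confirmatory scan ALSO shows RECIST progression, the initial scan will be recorded as the first date of progression".

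The sections that define the endpoint have no such condition:

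- Section 1.7.2: "While the official endpoint for this trial of concurrent axitinib/pembrolizumab in sarcomas will utilize RECIST v1.1".
- Section 14.1.4 defines progressive disease by the increase in the sum of diameters or by a new lesion, with no repeat scan.
- Section 14.2: "PFS is defined as the time from treatment initiation until documented disease progression or death". On censoring it says: "In progression-free patients, PFS will be censored at the last evaluable tumor assessment (RECIST v1.1".
- Section 16.2: "The primary endpoint will be the progression-free survival by RECIST 1.1 in evaluable patients".
- Section 16.3 plans Kaplan-Meier estimates at times such as 3, 6 and 12 months with log-log 95% intervals, and does not mention the exception.

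The only response criteria in the document with a confirmation step for progression are the exploratory immune-related criteria (Appendix F, Table F4).

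**The concern.** The event that decides the primary result is described in two ways. Under sections 14.1.4 and 14.2 the first RECIST progression ends PFS. Under section 11.0, for a subset of patients, dating the event at that scan depends on a later scan.

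Entry to the subset rests on the investigator's opinion in an open-label, single-arm study. Patients taken off treatment at first progression keep their event, while patients kept on may lose it or have it dated later. A rule of this kind cannot add events. Two analysts following the same document could therefore report different primary results from the same data, and any difference would favour the treatment. The exploratory biomarker analyses in section 16.3 that use 3-month progression-free status would inherit the same ambiguity.

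**Working it through.** **1. The plan's own figure.** Section 16.4 gives 97.5% power with 40 evaluable patients, 3-month PFS of 19% versus 40%, a one-sample survival test at one-sided 5%, 15 months' accrual and 12 months' minimum follow-up. Under exponential survival:

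- Null hazard = −ln(0.19)/3 = 0.5536 per month; alternative hazard = −ln(0.40)/3 = 0.3054; ratio = 0.552.
- Nearly all 40 patients have an event, so power ≈ Φ(√40 × |ln 0.552| − 1.645), which gives 98.2%. An exact gamma test gives 98.0% and a test on mean survival 97.3%.

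The stated power reproduces. It makes no allowance for progressions left uncounted.

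**2. The two rules side by side**, for a patient with a first RECIST 1.1 progression:

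| Situation | Section 11.0 | Sections 14.1.4 and 14.2 |
|---|---|---|
| Treatment stopped | Exception does not apply; event at first scan | Event at first scan |
| Kept on, 6-week scan confirms | Event at first scan | Event at first scan |
| Kept on, 6-week scan does not confirm | Not stated; condition unmet, so by implication no event at first scan | Event at first scan |
| Kept on, 6-week scan not done (death, decline, withdrawal, new therapy) | Not stated | Event at first scan |

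The rules agree in the first two rows and can diverge in the last two.

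**3. Does this reach the 3-month estimate?** Sections 12.2 and 14.1 put imaging at 84 ± 7 days from enrollment, that is, days 77 to 91. The enrollment procedures require treatment to start within 7 days of enrollment. The first scan therefore falls between 77 − 7 = 70 and 91 − 0 = 91 days after treatment start, against 365.25/4 = 91.3 days for 3 months. By the cycle calendar, cycle 3 day 1 is nominally day 49 + 42 + 1 = 92, or 91 elapsed days. Most of the window is inside 3 months; late scans can fall outside it. The 6-month, 12-month and median PFS are exposed in any case.

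**4. Size per patient.** With 40 patients and no censoring before 3 months, one uncounted progression moves the rate by 1/40 = 2.5 points. For the planned interval, with S = x/40, the standard error of ln(−ln S) is √[(1 − S)/(40S)] / |ln S|, and the lower limit is exp{−exp[ln(−ln S) + 1.96 × SE]}:

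- 13/40: S = 0.325, SE = 0.203, 95% CI 18.8% to 47.0%.
- 14/40: S = 0.350, SE = 0.205, 95% CI 20.8% to 49.6%.

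Here one patient carries the lower limit across 19%.

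**5. A scenario, not an estimate.** Let q be the assumed share of 3-month failures whose first progression goes uncounted. A true 19% then reads as 0.19 + 0.81q: 21.0%, 23.1% and 27.1% for q = 2.5%, 5% and 10%. Under an exact binomial test at 3 months (13 or more of 40 needed), the false-positive rate goes from 3.0% to 6.1%, 11.2% and 27.2%. No value of q is in the documents. The binomial test is not the planned test. The formula treats all 81% of failures as progressions that could be reclassified, although deaths without progression could not be.

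**The case against.** The strongest reply is that section 11.0 covers only the confirmed case. There it guards against bias, because it stops the later scan date being used when treatment continues. Nothing written says that an unconfirmed progression is discarded, and the sections that define the endpoint would count it. This stands in part: a reader might infer that the plan drops unconfirmed progressions, but that is implied, not written. It does not remove the conflict. If the first progression always counted, the condition in section 11.0 would serve no purpose.

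A reader might also infer that the 3-month rate is shown to be biased upward against the historical 19%. The documents do not support that. Sections 7.0 and 16.4 give the 19% without the progression rule behind it, so a mismatch is possible but not established.

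Timing is a fair limit: a progression first seen after 91.3 days is outside the 3-month estimate under either rule. Step 3 shows that this narrows the effect without removing it.

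Finally, the exception points particularly to cases where immune-related criteria, Choi criteria or MRI volumetrics would not require stopping, and section 13.4 and Appendix F plan blinded reading for these. The rationale, pseudoprogression, is set out in section 1.7.2. Even so, the stated test for entry is the investigator's opinion, and Appendix F has the investigators making the standard tumor measurements.

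**Conclusion.** The point holds as a conflict between rules for the primary event, with one branch left undefined. Section 11.0 conditions the progression date on confirmation for a subset chosen at the investigator's discretion; sections 14.1.4, 14.2, 16.2 and 16.3 do not. If unconfirmed progressions go uncounted, PFS can only rise. The size is 2.5 points on the 3-month rate per patient whose first scan falls before 3 months, assuming 40 evaluable patients and no earlier censoring. At that sample size one patient can matter, as the step from 13/40 to 14/40 shows.

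The total effect cannot be stated, because the number of patients affected is not given. The false-positive rates in step 5 show sensitivity to an assumed frequency and should not be read as the trial's error rate. The stated power is not in dispute.

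**What to change.** In sections 11.0, 14.2 and 16.3, state that the primary PFS event is the first RECIST 1.1 progression, or death, for every patient, whether or not treatment continues and whether or not a later scan confirms the progression or is missing. Report PFS based on confirmed progression as a sensitivity analysis, with the number of patients whose event status or date differs and the handling of a missing second scan written down.

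The rule on continuing treatment after progression is left as it is. The cost is a sentence in each of three sections and one extra analysis; the reported PFS may be slightly less favourable.
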